## **8.0 Subject Disposition**

The number and percentage of subjects who screen failed for any reason, and for each screen fail reason, will be summarized for all subjects who screen failed.

### **8.1 Disposition of Safety Population**

The number of subjects in each of the following categories will be summarized overall and by investigator.

- Subjects enrolled in this study;
- Subjects who took at least one dose of study drug;
- Subjects who completed study drug;
- Subjects who prematurely discontinued study drug;
- Subjects who completed the study;
- Subjects who prematurely discontinued from the study;
- Subjects ongoing in the PT Period at the time of the planned analysis.

The number and percentage of subjects who discontinued study drug will be summarized by reason (all reasons) and by primary reason (per eCRF). Similar summaries will be provided for discontinuations from the study.

The number and percentage of subjects with reported study drug interruptions will be summarized.

Reasons for study drug interruptions will be presented in the CSR listings.

## **9.0 Study Drug Exposure and Compliance**

### **9.1 Exposure**

The duration of exposure to study drug will be summarized in the safety population. Duration of exposure is defined for each subject as the last study drug dose date minus the first study drug dose date plus 1 day.

Descriptive statistics (mean, standard deviation, median, minimum, and maximum) will be presented for exposure during the treatment period.

Study drug duration also will be summarized with frequencies and percentages using the following categories:

- 1 to 15 days, 16 to 35 days, 36 to 51 days,  $\geq 52$  days.

### **9.2 Compliance**

At each visit (starting with the Week 4 visit) during the Treatment Period, the total number of tablets dispensed and returned is recorded. The compliance for study drug (GLE/PIB) during the treatment period will be calculated as the percentage of tablets taken relative to the total tablets expected to be taken. The total number of tablets expected to be taken will be equal to the total number of tablets that should have been taken per the protocol for the duration that the subject was in the Treatment Period (date of last dose of study drug – date of first dose of study drug + 1). Study drug interruptions recorded on the eCRF will not be subtracted from the duration.

A subject is considered to be compliant if the percentage is between 80% and 120%. Compliance will be calculated for each subject and summarized with the mean, median, standard deviation, minimum, and maximum. The percentage of compliant subjects will be summarized based on data as observed. An additional summary of the percentage of compliant subjects will be provided where subjects who are missing study drug accountability records will be imputed as non-compliant.

## 10.0 Efficacy Analysis

### 10.1 General Considerations

All efficacy analyses will be performed on the ITT population, unless otherwise specified.

Missing data will be imputed as described in Section 6.3 for analyses of the HCV RNA endpoints of SVR.

Plasma HCV RNA levels will be determined for each sample collected by the central laboratory using the Roche COBAS® AmpliPrep/COBAS® TaqMan® Quantitative HCV Test, v2.0. The lower limit of detection (LLOD) and lower limit of quantification (LLOQ) for this assay (regardless of genotype) are both 15 IU/mL.

HCV RNA results that are detectable but not quantifiable are reported as "< 15 IU/ML HCV RNA DETECTED" and those that are undetectable are reported as "HCV RNA NOT DETECTED" in the database.

The notation "HCV RNA < LLOQ" is used to represent all HCV RNA values < 15 IU/mL, including values reported as "HCV RNA NOT DETECTED" or "< 15 IU/ML HCV RNA DETECTED." HCV RNA  $\geq$  LLOQ are all quantifiable values of 15 IU/mL or greater.

IL28B rs12979860 will be resulted as C/C, C/T, or T/T by the central laboratory.

#### **Definitions for Efficacy Endpoints**

A confirmed quantifiable value during treatment is defined as any two consecutive HCV RNA measurements  $\geq$  LLOQ (or 100 IU/mL for **Breakthrough**), either both during treatment or at the final treatment measurement and the next consecutive post-treatment measurement. A confirmed quantifiable post-treatment value is defined as any two consecutive post-treatment HCV RNA measurements  $\geq$  LLOQ.

**Breakthrough** = confirmed HCV RNA  $\geq$  100 IU/mL after HCV RNA  $<$  LLOQ during the Treatment Period; or confirmed increase from nadir in HCV RNA (two consecutive HCV RNA measurements  $>$  1  $\log_{10}$  IU/mL above nadir) at any time point during the Treatment Period. A single breakthrough value ( $\geq$  100 IU/mL or  $>$  1  $\log_{10}$  above nadir) followed by lost to follow-up also will be considered a breakthrough (i.e., will not require confirmation).

**EOT failure** = HCV RNA  $\geq$  LLOQ at end of treatment with at least 6 weeks of treatment, where the HCV RNA value must be collected on or after Study Drug Day 36 and study drug duration  $\geq$  36 days.

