8.1.2.2.2 Other Secondary Efficacy Endpoints

The other secondary efficacy analyses, which are not included in the fixed sequence, are listed below:

- The percentage of HCV GT3-infected subjects in the PP population who achieve SVR₁₂;
- The percentage of HCV GT3-infected subjects in the ITT population who achieve SVR₁₂;
- The percentage of subjects with OTVF (defined as confirmed increase of $> 1 \log_{10}$ IU/mL above nadir during treatment, confirmed HCV RNA ≥ 100 IU/mL after HCV RNA $<$ LLOQ during treatment, or HCV RNA \geq LLOQ at the end of treatment with at least 6 weeks of treatment), and
- The percentage of subjects with post-treatment relapse (Relapse₁₂: defined as confirmed HCV RNA \geq LLOQ between end of treatment and 12 weeks after the last dose of study drug [up to and including the SVR₁₂ assessment time point] among subjects who completed treatment as planned [defined as study drug duration \geq 52 days for subjects assigned to 8 weeks of treatment] with HCV RNA $<$ LLOQ at the end of treatment; excluding subjects who have been shown to be reinfected).

For the analyses of SVR₁₂ among HCV GT3-infected subjects, the number and percentage of subjects achieving SVR₁₂ will be summarized along with a two-sided 95% confidence interval using Wilson's score method.

For the analysis of OTVF and post-treatment relapse, the number and percentage of subjects in the ITT population will be summarized along with a two-sided 95% confidence interval using Wilson's score method. Separate summaries will be provided for all subjects across genotypes, within HCV GT1, 2, 4, 5, and 6-infected subjects combined, and within HCV GT3-infected subjects.

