#### **5.1.2 Per Protocol (PP) Population**

All subjects who receive at least one dose of study drug, with the exception of subjects who experience breakthrough, or prematurely discontinue treatment prior to Week 8, or have no HCV RNA value in the SVR12 visit window or later will be included in the PP population. In other words, the per protocol population includes all subjects in the ITT population, with the exception of subjects who prematurely discontinue prior to Week 8 (subjects with treatment duration < 52 days), subjects who experience virologic failure prior to Week 8 (subjects with **on-treatment virologic failure** before Study Day 52), subjects without virologic failure who have no HCV RNA value in the SVR12 visit window or later, and subjects who are SVR12 non-responders due to re-infection. Subjects who have HCV GT3 infection will be excluded from the PP analysis of HCV GT1, 2, 4, 5, and 6-infected subjects.

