#### 10.4.2 Other Secondary Efficacy Analyses

The other secondary efficacy analyses, which are not included in the fixed sequence, are listed below:

- The percentage of HCV GT3-infected subjects in the PP population who achieve SVR12;
- The percentage of HCV GT3-infected subjects in the ITT population who achieve SVR12;
- The percentage of subjects in the ITT population with on-treatment virologic failure (defined as **On-treatment virologic failure**), and
- The percentage of subjects in the ITT population with post-treatment relapse (defined as **Relapse**12; subjects with reinfection will be summarized separately).

For the analyses of SVR12 among HCV GT3-infected subjects, the number and percentage of subjects achieving SVR12 will be summarized along with a two-sided 95% confidence interval using Wilson's score method.

For the analysis of on-treatment virologic failure and post-treatment relapse, the number and percentage of subjects in the ITT population will be summarized along with a two-sided 95% confidence interval using Wilson's score method.

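### SAP 5.1.2 widens the per-protocol exclusion from breakthrough to any on-treatment virologic failure before Day 52, so one unconfirmed end-of-treatment value can remove a treatment completer from the first primary analysis; the same value can count an SVR12 responder as a virologic failure

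*SAP*

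**What the plan says.** **EOT failure.** SAP 10.1 defines it as HCV RNA at or above the "LLOQ at end of treatment with at least 6 weeks of treatment". The same definition then sets a timing condition, "where the HCV RNA value must be collected on or after Study Drug Day 36 and study drug duration" being at least 36 days. Values at or above the "LLOQ are all quantifiable values of 15 IU/mL or greater". No second value is required. Protocol 8.1.2.2.2 also sets this component at HCV RNA at or above the "LLOQ at the end of treatment with at least 6 weeks of treatment", without confirmation, while its two breakthrough components must be confirmed.

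**Confirmation.** SAP 10.1 defines a confirmed quantifiable on-treatment value as two consecutive values, "either both during treatment or at the final treatment measurement and the next consecutive post-treatment measurement". The EOT-failure definition does not invoke this.

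**OTVF and SVR12.** OTVF is breakthrough or EOT failure. SVR12 looks only at post-treatment values. SAP 10.4.2 reports "The percentage of subjects in the ITT population with on-treatment virologic failure", with no restriction to SVR12 non-responders.

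**PP population.** Protocol 8.1 and the first sentence of SAP 5.1.2 exclude subjects with breakthrough, subjects who discontinue before Week 8, and subjects with no HCV RNA value in the SVR12 window or later. The second sentence of SAP 5.1.2, offered as a restatement, excludes "subjects who experience virologic failure prior to Week 8" and explains this as OTVF before Study Day 52. It also excludes subjects with treatment duration below 52 days.

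**The concern.** The restatement in SAP 5.1.2 is not equivalent to the rule it restates, because EOT failure belongs to OTVF but not to breakthrough. The PP analysis in genotypes 1, 2, 4, 5 and 6 opens the fixed sequence: if it fails, nothing else is tested. SAP 10.3 justifies PP on the ground that excluded subjects fail for reasons that do not help to distinguish treatment durations. Quantifiable virus at the end of a shortened course is hard to describe that way.

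The second issue is agreement between tables. OTVF is a stated secondary objective. A responder with one EOT value just above the assay limit is counted in the OTVF rate. That subject also leaves the relapse analysis, which requires HCV RNA below LLOQ at the Final Treatment Visit, and meets the description of the primary virologic failure population in SAP 10.8. The table of reasons for SVR12 non-response (SAP 10.1) covers non-responders only, so the subject does not appear there.

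**Working it through.** **Inputs.** N = 270, assumed PP rate 98%, threshold 94%, stated power about 91% (Protocol 8.2). Interval: normal approximation, or Wilson if there are fewer than 5 failures (SAP 10.3). The final treatment value is the last value up to Study Drug End Day 2 (SAP 6.1.2). The Week 4 window is Days 22 to 42 and the Week 8 window Days 43 to 70 (SAP Table 1). I date an EOT failure by its sample day; the SAP does not say otherwise.

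**Stated power.** With the null variance:

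- Φ{[(0.98 − 0.94) − 1.96·√(0.94·0.06/270)] / √(0.98·0.02/270)} = Φ{(0.04 − 1.96·0.01445)/0.00852} = Φ(1.37) = 0.915, which agrees with 91%.
- Exact power with a Wilson lower bound (at most 8 failures) is 0.905.
- The interval rule the plan will use allows up to 10 failures at n = 270, with exact power 0.979. The pass/fail boundary therefore lies between 10 and 11 failures.

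**Who is affected by one EOT value of 15 IU/mL or more?**

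| Case | Study drug duration | Last on-treatment sample | Counted as OTVF | PP under SAP 5.1.2 |
|---|---|---|---|---|
| a | ≥ 52 days | Day 52 or later | yes, even if SVR12 achieved | stays in |
| b | 36–51 days | Day 36 or later | yes | already out (duration < 52 days) |
| c | ≥ 52 days | Days 36–51 | yes | out only because of the widened clause |

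Case c arises from an early Week 8 visit (for example, sample on Day 50 and dosing to Day 56), or from a late Week 4 sample with the Week 8 sample missing.

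**Case c, true virologic failure removed.** Lower bound = p − 1.96·√(p(1 − p)/n).

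- 259/270 = 0.95926; standard error 0.01203; lower bound 0.9357. Fails.
- 259/269 = 0.96283; standard error 0.01154; lower bound 0.9402. Passes.

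A flip from one removal needs exactly 11 failures in 270. At a true rate of 98% that has probability C(270,11)·0.02¹¹·0.98²⁵⁹ = 0.012, before requiring that one of the 11 be a case c subject.

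**Case c, responder removed.** With 5 failures, 265/270 = 98.15% (lower bound 96.54%) becomes 264/269 = 98.14% (96.53%), a change of about 0.01 point. Losing responders changes a pass to a fail only if 2 are lost with exactly 10 failures, 24 with 9, or 46 with 8.

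**OTVF rate, one responder counted (Wilson 95% interval).**

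| Group | Not counted | Counted |
|---|---|---|
| Genotypes 1, 2, 4, 5, 6 | 0/270: 0% (0 to 1.40) | 1/270: 0.37% (0.07 to 2.07) |
| Genotype 3 | 0/60: 0% (0 to 6.02) | 1/60: 1.67% (0.29 to 8.86) |

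Zero is a fair reference point, because Protocol 8.2.1 reports no virologic failure among 117 + 65 = 182 historical subjects.

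**The case against.** **The PP effect is confined to case c.** This stands. A normally timed Week 8 sample leaves the subject in PP, and short-duration subjects are excluded anyway. A reader might infer that losing cured subjects threatens the gating test. The figures above do not support that: the shift is tiny and works against success. The direction that matters is removal of a true failure.

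**An unconfirmed EOT failure is a defensible definition on which protocol and SAP agree.** This largely stands. Relapse also accepts a single value when it is the last one available. A reader might infer that every EOT failure should need the next value for confirmation. That would do harm. Take a completer with EOT at or above LLOQ, a Post-Treatment Week 4 value below LLOQ, and confirmed viraemia by Week 12. This subject would no longer be an EOT failure. Relapse and reinfection both require a Final Treatment Visit value below LLOQ, so without breakthrough the subject would fall into the category Other and leave the virologic-failure populations.

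**36 days is not 6 weeks.** A reader might infer a contradiction with the protocol's 6 weeks, which is 42 days. The plan allows a tolerance on every duration: 52 days for 56, and 77 for 84 (SAP 10.1). Taking 36 for 42 fits that pattern and is stated in the same sentence.

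**The consequences are limited.** OTVF is outside the fixed sequence, post-baseline sequencing of virologic failures needs at least 1000 IU/mL, and resistance Analysis 4 covers SVR12 non-responders only. All true, but the OTVF rate and the SVR12 non-response table can still disagree without explanation.

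**Conclusion.** Two limited defects stand.

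1. SAP 5.1.2 departs from the protocol's PP rule while presenting itself as a restatement. One EOT value on Days 36 to 51 can remove a treatment completer from the first primary analysis. At the boundary, one removed failure moves the lower bound from 93.57% to 94.02% and turns a fail into a pass.
2. An SVR12 responder can be counted as OTVF on one reading and dropped from the relapse denominator, with no matching entry among the reasons for non-response. One such subject adds 0.37 points to the OTVF rate in 270 subjects, or 1.67 points in 60.

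The documents give no rate of low-level EOT viraemia and no distribution of Week 8 sample days. I assume both cases are rare, of the order of 0 to 2 subjects. ITT SVR12 does not depend on OTVF and is unaffected. The change is still worth making before the analysis, because it is cheap and concerns who enters the gating test.

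**What to change.** 1. **SAP 5.1.2.** In the restating sentence, limit the virologic exclusion to breakthrough, as in Protocol 8.1. Keep the 52-day duration clause. EOT failure alone then does not remove a subject with study drug duration of 52 days or more.
2. **SAP 10.1 and 10.4.2.** Do not count an unconfirmed EOT value as OTVF when the subject achieves SVR12; report such subjects on a separate line. Keep the current EOT-failure rule for SVR12 non-responders, so that no true virologic failure moves into Other. State that a responder whose EOT value is confirmed by the next post-treatment value still counts as OTVF.
3. **Record the change.** Protocol 8.1.2.2.2 carries the unconfirmed definition, so note the refinement in SAP 12 or align the protocol text.

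The 36-day limit can stay. The cost is a few sentences and a small amount of programming, using samples already scheduled. The one downside is that OTVF status for a few subjects waits for their post-treatment results.

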**On-Treatment Virologic Failure = Breakthrough or EOT Failure.**

**SVR4** = HCV RNA  $<$  LLOQ in the SVR4 window (4 weeks after the last actual dose of study drug) without any confirmed quantifiable ( $\geq$  LLOQ) post-treatment value before or during that SVR window.

**SVR12** = HCV RNA  $<$  LLOQ in the SVR12 window (12 weeks after the last actual dose of study drug) without any confirmed quantifiable ( $\geq$  LLOQ) post-treatment value before or during that SVR window.

**SVR24** = HCV RNA  $<$  LLOQ in the SVR24 window (24 weeks after the last actual dose of study drug) without any confirmed quantifiable ( $\geq$  LLOQ) post-treatment value before or during that SVR window.

**Relapse12** = confirmed HCV RNA  $\geq$  LLOQ between end of treatment and 12 weeks after last actual dose of study drug (up to and including the SVR12 assessment time point) for a subject with HCV RNA  $<$  LLOQ at Final Treatment Visit who completed treatment and has post treatment HCV RNA data available, excluding reinfection as described below.

**Relapse24** = confirmed HCV RNA  $\geq$  LLOQ during SVR24 window among subjects who achieved SVR12 and have HCV RNA data available during the SVR24 window, excluding reinfection as described below.

**Relapseoverall** = confirmed HCV RNA  $\geq$  LLOQ between end of treatment and up to and including the last HCV RNA measurement collected in the PT Period for a subject with HCV RNA  $<$  LLOQ at Final Treatment Visit who completed treatment and has post treatment HCV RNA data available, excluding reinfection as described below.

Only subjects who have at least one post-treatment HCV RNA value will be included in analyses of relapse. For relapse analyses, the completion of treatment is defined as a study drug duration  $\geq$  52 days for subjects assigned to 8 weeks of treatment. If the regimen is extended to 12 weeks for some subjects, then those subjects will be considered completers if they have a study duration  $\geq$  77 days. If the last available post-treatment value is  $\geq$  LLOQ, then the subject will be considered a relapse (i.e., will not require confirmation).

HCV reinfection is defined as confirmed HCV RNA  $\geq$  LLOQ after the end of treatment in a subject who had HCV RNA  $<$  LLOQ at Final Treatment Visit, along with the post-treatment detection of a different HCV genotype, subtype, or clade compared with baseline, as determined by phylogenetic analysis of the NS3 or NS5A, and/or NS5B gene sequences. Reinfection in the case of the same HCV subtype is defined as a clade switch, as indicated by the lack of clustering between the baseline and post-treatment sequences by phylogenetic analysis. If phylogenetic analysis is not possible due to technical difficulties, HCV reinfection may be determined with a confirmed HCV genotype or subtype switch by the Versant HCV Genotype Inno-LiPA Assay v2.0 or Sanger assay.

Post-treatment relapse is defined as described earlier (**Relapse12**, **Relapse24**, **Relapseoverall**), and no genotype, subtype, or clade switch compared with baseline as determined by phylogenetic analysis of the NS3 or NS5A gene sequences. If phylogenetic analysis is not possible due to technical difficulties, the subject will be defined as having a post-treatment relapse unless an HCV genotype or subtype switch is confirmed by the Versant HCV Genotype Inno-LiPA Assay v2.0 or Sanger assay.

### **Reasons for SVR12 Non-Response**

Subjects who do not achieve SVR12 (SVR12 non-responders) will be categorized as having:

1. On-treatment virologic failure (see **On-treatment virologic failure** definition, if a subject meets both definitions of **Breakthrough** and **EOT failure**, he or she will be categorized as **Breakthrough** only);
2. HCV reinfection (see definition described earlier);
3. Relapse12 (see **Relapse12** definition);
4. Prematurely discontinued study drug with no on-treatment virologic failure (defined as any SVR12 non-responder who prematurely discontinued study drug [study drug duration < 52 days for subjects assigned to 8 weeks of treatment, and < 77 days for subjects extended to 12 weeks of treatment] and did not meet the **On-treatment virologic failure** definition);
5. Missing follow-up data in the SVR12 window (defined as any subject who completed study drug without data in the SVR12 window after applying the imputation rules and not meeting the definitions of [1], [2], [3], or [4]);
6. Other (defined as any SVR12 non-responder not meeting the definitions of [1] – [5]).

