### **6.3 Missing Data Imputation**

#### **Missing Data Imputation for SVR**

HCV RNA values will be selected for analysis based on the analysis windows defined in Section 6.2.

For analyses of SVR, subjects missing visit values will have backward imputation applied, if possible. For backward imputation, if the nearest HCV RNA value after the SVR window is unquantifiable or undetectable, then it will be used to impute the HCV RNA value in the SVR window. If a subject is missing an HCV RNA value within the appropriate SVR window after performing backward imputation, then this value will be imputed with an HCV RNA value from a local laboratory if present; otherwise, the HCV RNA value will be missing. Subjects with missing HCV RNA data in the analysis window, after imputations, will be imputed as a failure.

Regardless of the imputation method described above, if a subject starts another treatment for HCV, then all HCV RNA values for this subject measured on or after the start date of the new HCV treatment will be excluded from analyses. The subject will be considered a failure for summaries of viral response at all time points after the start of the new HCV treatment.

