## 10.8 Resistance Analyses

For all subjects, full length NS3/4A or NS5A from baseline samples will be sequenced by next generation sequencing (NGS). For subjects who experience virologic failure (on-treatment virologic failure or post-treatment relapse as defined in Section 10.1), full length NS3/4A and NS5A genes from the first sample after virologic failure with HCV RNA  $\geq$  1000 IU/mL will be sequenced by NGS. An appropriate subtype specific prototypic reference sequence will be used for comparison with sequences from samples. Subjects who experience virologic failure (VF) will be referred to as subjects in the primary virologic failure (PVF) population, and a listing by subject that includes HCV genotype/subtype, IL28B genotype, reason for SVR12 non-response, time point(s) sequenced as closest to time of VF, and HCV RNA value at the VF time point(s) will be produced for these subjects. In addition, all listings described below will display HCV genotype/subtype and reason for SVR12 non-response in the subject identifier for each subject. A separate listing will summarize all subjects in the PVF population for whom no sequencing was performed (e.g., lost to follow-up while HCV RNA  $\leq$  1000 IU/mL).

Subjects treated with study drug who do not achieve SVR12 due to reasons other than virologic failure (prematurely discontinued study drug with no on-treatment virologic failure, HCV reinfection, missing SVR12 data, or other reasons as described in Section 10.1, Reasons for SVR12 Non-Response), but have a time point with HCV RNA  $\geq$  1000 IU/mL after treatment discontinuation will have the sample at that time point sequenced. These subjects will be referred to as the non-PVF population. A listing of all subjects in the non-PVF population with post-baseline sequencing available will be created that is similar to the listing of subjects in the PVF population with post-baseline sequencing available.

Included time points for analyses on samples from subjects who do not achieve SVR12 are 1) the sample closest in time after failure/discontinuation with an HCV RNA level of  $\geq$  1000 IU/mL, and 2) 24 weeks post-DAA treatment, provided that resistance-associated substitutions were detected by NGS at the time of HCV virologic failure/treatment discontinuation.

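### A treatment completer first found viraemic after the SVR12 window meets Relapse_overall but is labelled as missing data, and the SAP then handles that subject in conflicting ways

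*SAP*

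**What the plan says.** The rules that meet on this subject are all in the SAP.

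- **Window (Section 6.2, Table 2).** SVR12 uses Study Drug End Days 57 to 126. SVR24 uses Days 127 to 210.
- **Imputation (Section 6.3).** A gap is filled backward only on a condition: "if the nearest HCV RNA value after the SVR window is unquantifiable or undetectable, then it will be used to impute" the missing value. Failing that, a local laboratory value is used. If the window is still empty, the subject is an SVR12 failure.
- **Relapse12 (Section 10.1).** It covers the time "between end of treatment and 12 weeks after last actual dose of study drug (up to and including the" SVR12 assessment. Protocol Sections 5.4.1.1 and 8.1.2.2.2 set the same limit.
- **Relapse24.** It is counted in the SVR24 "window among subjects who achieved" SVR12.
- **Relapse_overall.** It runs "between end of treatment and up to and including the last HCV RNA measurement collected in the PT Period".
- **Unconfirmed last value.** If the last available post-treatment value is quantifiable, "then the subject will be considered a relapse (i.e., will not require confirmation").
- **Category 5 of the SVR12 reasons.** It takes completers with no data in the SVR12 "window after applying the imputation rules and not meeting the definitions of [1], [2], [3], or [4". Item [3] is Relapse12; Relapse_overall is not named.
- **Resistance (Section 10.8).** The PVF population is defined by virologic failure, that is "on-treatment virologic failure or post-treatment relapse as defined in Section 10.1". The non-PVF population covers failures for other reasons, and missing SVR12 data is listed among those reasons.

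**The concern.** Relapse is a secondary objective, and Protocol Section 3.2 says that the shorter course may bring more virologic failure. For one pattern of visits, the SAP records a quantifiable post-treatment HCV RNA value but gives the SVR12 failure a reason that Section 10.8 treats as non-virologic. Other outputs use that reason. What is at stake is the consistency of the reasons table, mITT-GT-VF (which also feeds the subgroup, regression and resistance analyses), the PVF and non-PVF listings, and one sensitivity analysis that turns the subject into a responder.

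**Working it through.** The plan states no figure on this point, so there is nothing to reproduce first. The check traces one subject through the rules.

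**Subject.** Study drug for at least 52 days; below LLOQ at the Final Treatment Visit; PT Week 4 below LLOQ or not done; no central or local value in Days 57 to 126; next and last value at or above LLOQ in Days 127 to 210; no reinfection; no new HCV treatment.

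| Rule | Result |
|---|---|
| Backward imputation (6.3) | Not available, because the later value is quantifiable; SVR12 failure |
| Relapse12 (10.1) | Not met; the value is after its time limit |
| Relapse24 (10.1) | Not met; SVR12 was not achieved |
| Relapse_overall (10.1) | Met; confirmation is waived for a last value |
| SVR12 reason (10.1) | Category 5, missing follow-up |
| SVR24 reason (10.1) | Category 7, Other |
| PP (5.1.2) | Kept, as a failure; a value exists after the window |
| ITT | Failure |
| mITT-GT-VF (5.1.4) | Unclear: in if Relapse_overall makes this a virologic failure (10.1, 10.8); out if category 5 is non-virologic (10.8) |
| PVF and non-PVF (10.8) | Fits both if the late sample is at least 1000 IU/mL |
| 10.5.1, second approach | SVR12 success, because category 5 is recoded as success |

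The first approach in 10.5.1 also gives a success, because it carries forward the earlier value below LLOQ. That follows from its design and does not depend on the category 5 label.

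**Neighbouring patterns that do not reach this gap:**
- PT Week 4 also quantifiable: Relapse12.
- Reinfection: category 2.
- Less than 52 days of drug: category 4.
- Late value below LLOQ: SVR12 by backward imputation.
- Late value after Day 210 with nothing in Days 127 to 210: the same SVR12 label, but the SVR24 label becomes missing follow-up.

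**Size of one case.** With the planned numbers as approximate denominators, 1/270 = 0.37 points in non-GT3 and 1/60 = 1.67 points in GT3.

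**Illustration.** The counts are assumed: N = 270, all with eligible genotypes, 5 Relapse12 failures, k subjects of this type, no other failures.

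| k | mITT-GT-VF, subject out | mITT-GT-VF, subject in | 10.5.1 second approach | Relapse12 | Relapse12 plus late cases |
|---|---|---|---|---|---|
| 1 | 264/269 = 98.1% | 264/270 = 97.8% | 265/270 = 98.1% | 5/270 = 1.9% | 6/270 = 2.2% |
| 2 | 263/268 = 98.1% | 263/270 = 97.4% | 265/270 = 98.1% | 5/270 = 1.9% | 7/270 = 2.6% |
| 3 | 262/267 = 98.1% | 262/270 = 97.0% | 265/270 = 98.1% | 5/270 = 1.9% | 8/270 = 3.0% |

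ITT is 264/270, 263/270 and 262/270 whichever label is used.

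**How often.** Protocol Section 8.2.1 gives 117 + 65 = 182 historical subjects, two of them with missing SVR12 data, and a PP rate of 100%. The PP rule removes a missing-data subject only when there is no value in the window or later. A subject with a later quantifiable value would have stayed in PP as a failure, and the rate would have been below 100%. The historical count on this path is therefore 0/182.

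**The case against.** The strongest reply has four parts.

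1. **The case is not hidden.** Section 10.7 summarises Relapse_overall by the window of first relapse, with subject numbers, and Section 4.4.1 counts relapse at any post-treatment visit for the futility monitoring. This stands. The outputs contradict one another; they do not conceal the event.
2. **Week 12 status really is unknown.** A value below LLOQ at Week 24 supports response at Week 12, whereas a quantifiable one does not prove viraemia at Week 12. The missing label is literally true of the window, and scoring failure in ITT and PP is the unfavourable choice. This also stands. It does not justify recoding the subject as a success, or leaving the resistance population undecided.
3. **The last-value sentence may already make the subject a relapse.** Its own parenthesis limits it to waiving confirmation. It neither says which relapse definition applies nor lifts the Relapse12 limit.
4. **The 12-week limit comes from the protocol.** This stands, and it rules out widening Relapse12 in the SAP alone.

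A reader might also infer a frequency from the two historical subjects with missing data: 2/182 × 330 = 3.6 subjects. The documents do not support that figure, because being on this path requires a later quantifiable value, which neither subject can have had if the PP rate was 100%. Nor do they support saying that mITT-GT-VF is certainly inflated, since the text can be read either way.

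**Conclusion.** The gap is real and confined to secondary and sensitivity outputs. A completer first quantifiable after Day 126, with no value in the SVR12 window, is a relapse under one SAP definition and missing data under another. The downstream rules then disagree, and one of them counts a subject with observed viraemia as a responder. The primary and key secondary ITT and PP results are the same under either label.

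The expected number is unknown. The historical 0/182 comes from 12 weeks of treatment with no virologic failure, so it gives no rate for 8 weeks, but nothing in the documents suggests more than a few cases. One case is worth about 0.4 points in non-GT3 and 1.7 points in GT3, where about 60 subjects are planned. These sizes take the planned numbers as denominators; the relapse analyses require at least one post-treatment value and completed treatment, so the true denominators will be slightly smaller. The reading of 0/182 assumes that the historical PP population followed the definition printed in the protocol.

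**What to change.** Leave Relapse12 as the protocol defines it. In SAP Section 10.1:

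- Add to the SVR12 and SVR24 non-response lists a reason such as 'relapse first detected after the SVR12 window', ranked above missing follow-up. It should cover completers with no value in the SVR12 window who meet Relapse_overall before any new HCV treatment.
- Add to category 5 of the SVR12 list that the subject must not meet Relapse_overall.

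Then state that these subjects:

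- are virologic failures for mITT-GT-VF (Section 5.1.4);
- belong to PVF and not to non-PVF (Section 10.8);
- are not counted as successes in Section 10.5.1. The first approach there needs its own sentence, because it works on values and not on categories;
- are shown beside the Relapse12 rate, so that the two relapse figures can be reconciled.

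The cost is a few lines of SAP text and programming, with no new data. Some secondary or sensitivity figures may become slightly less favourable.
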